10. SAFETY

Analysis Set: Full Analysis Set (FAS)

10.1 Safety Endpoints

- Number of AEs, SAEs, ADRs, severe AEs and AEs leading to treatment discontinuation during the trial period.
- Change in WBC and differentials in blood from Baseline to Weeks 4, 12, 24, 32, 40, 48 and 12-week follow-up.
- Change in DLCO from Baseline to Weeks 4, 8, 12, 16, 20, 24, 32, 40, 48 and at 12-week follow-up.
- Change in forced expiratory volume in 1 second (FEV1) (% predicted) and forced vital capacity (FVC) (% predicted) from Baseline to Weeks 12, 24, 32, 40 and 48.
- Development of anti GM-CSF antibodies at Week 4, 12, 24, 32, 48 and at 12-week follow-up.

10.2 Adverse Events

10.2.1 *Definition of variables*

- AE, any untoward medical occurrence in a subject or clinical trial subject administered a medicinal product and which does not necessarily have a causal relationship with this treatment.
- Treatment Emergent Adverse Event (TEAE), defined as an AE that commences on, or after, the date of the first administration of study drug until and including the day of the 12-week Follow-up visit.
- Serious Adverse Event (SAE), as defined in the protocol section 12.16:
 - Results in death
 - Is life-threatening
 - Requires hospitalization or prolongation of existing hospitalization
 - Results in persistent or significant disability or incapacity
 - Is a congenital anomaly or birth defect
 - May jeopardize the subject or may require intervention to prevent one or more of the other outcomes listed above (Important Medical Events)
- Severity
 - Mild
 - Moderate
 - Severe
- Outcome
 - Not Recovered
 - Recovered
 - Recovered with Sequelae
 - Fatal
 - Unknown
- Causality, categorised as described in the protocol section 12.16:
 - Not applicable
 - Unlikely
 - Possible
 - Probable
- Causality (Binary categorisation), where:
 - Not related = Not Related or Unlikely
 - Related = Possible or Probable

- Actions taken with study drug
 - Dose delayed
 - Dose stopped
 - Treatment withdrawn
- Other actions taken
 - Medical procedure
 - Medication administered
 - Other

10.2.2 *Biostatistical methods*

Adverse events will be coded using Medical Dictionary for Regulatory Activities (MedDRA).

All adverse events recorded during the study will be listed. All serious AE and AEs leading to treatment discontinuation and study withdrawal will be listed.

Summary tables will be produced for treatment emergent adverse events (TEAEs). The number and percentage of subjects with adverse events by system organ class (SOC) and preferred term (PT) will be tabulated. Similar summaries will be produced by severity and relatedness.

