### 3. TRIAL FLOW CHART

**Table 1: Study Schedule of Assessments**

| Visit number                           | V1        | V2                | V3               | V4               | V5               | V6                | V7                | V8                | V9 h   | V10               | V11 h  | V12               | V13               | V14               | V15               | UV                             |
|--|-----------|-------------------|------------------|------------------|------------------|-------------------|-------------------|-------------------|-------------------|-------------------|-------------------|-------------------|-------------------|-------------------|-------------------|--------------------------------|
|  | Screening | Base-line         | Week 4           | Week 8           | Week 12          | Week 16           | Week 20           | Week 24           | Week 28 TC        | Week 32           | Week 36 TC        | Week 40           | Week 44 TC        | Week 48           | 12-Week F-up      | Unscheduled visit a |
| Day                                    |           | < 10 wks after V1 | 28 days after V2 | 56 days after V2 | 84 days after V2 | 112 days after V2 | 140 days after V2 | 168 days after V2 | 196 days after V2 | 224 days after V2 | 252 days after V2 | 280 days after V2 | 308 days after V2 | 336 days after V2 | 84 days after V14 |                                |
| Window                                 |           |                   | ± 7 Days         | ± 7 Days         | ± 7 Days         | ± 7 Days          | ± 7 Days          | ± 7 Days          | ± 7 Days          | ± 7 Days          | ± 7 Days          | ± 7 Days          | ± 7 Days          | ± 7 Days          | ± 7 Days          | ± 7 Days                       |
| Informed consent                       | X         |                   |                  |                  |                  |                   |                   |                   |                   |                   |                   |                   |                   |                   |                   |                                |

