Participating subjects will be encouraged to contact the clinic between visits if they experience adverse events (AEs), worsening of their condition or have any other concerns. If needed, unscheduled visits will be conducted at investigator's discretion.

A schedule of study assessments is available in [Table 1](#).

Treatment with inhaled molgramostim will be given at a dosage of 300 µg once daily for 48 weeks. All subjects in the trial initially consented to 24 weeks of treatment. All enrolled subjects continuing with 48 weeks of treatment will re-consent and follow the visits schedule as described above.

Subjects that do not wish to continue to 48 weeks of treatment will end treatment after 24 weeks (visit 8) and will attend the follow-up visit 12-weeks later as per the visit schedule outlined in Protocol Version 2.0 or 3.0.

Subjects who complete the initial 24-week treatment period prior to the approval of Protocol Version 4.0 will proceed to the 12 week follow up as per the visit schedule in Protocol Version 2.0 or 3.0. Once Protocol Version 4.0 is approved they will be asked to re consent and re-initiate treatment. This will occur at the next trial visit or at an unscheduled visit. These subjects will not receive the whole 48-week treatment. They will receive treatment for an additional 24 weeks minus the number of weeks that they have been in follow up.

Subjects that do not wish to re consent and re initiate treatment will stay in follow up and attend the follow-up visit as per the visit schedule outlined in Protocol Version 2.0 or 3.0.

At Baseline and at Weeks 4, 12, 24, 32 and 40 (Visits 2, 3, 5, 8, 10 and 12), dosing will take place in the clinic after blood sampling. A data review was conducted after the first 6 subjects had completed 12 weeks of treatment. If safety concerns or poor tolerability were identified in this review, the review committee might decide on less frequent dosing for subsequent subjects

in the study. The review was conducted on 16 September 2018 and concluded that there were no safety issues of significant concern and the dose was unchanged. In order to obtain more robust treatment responses it was decided to extend the treatment duration from 24 to 48 weeks. Any changes to the conduct of the study such as change of dose, dose regimen or duration will be documented in a protocol amendment.

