### **9.3. Subject Withdrawal Criteria**

#### **9.3.1. Discontinuation from Trial Treatment**

Subjects may be discontinued from treatment and assessments at any time, if deemed necessary by the investigator.

Potential reasons for discontinuation of treatment are:

- Lack of efficacy/worsening of disease
- Unacceptable AE
- Serious hypersensitivity reaction
- Pregnancy

Those who discontinue treatment will not automatically be withdrawn from the trial but will be encouraged to continue to follow the same visit schedule. For example: if treatment is discontinued at Week 4 (Visit 3) the subject will be encouraged to attend the remaining visits.

The reason and date the subject is discontinued from treatment will be documented in the electronic case report form (eCRF).

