2. PROJECT OVERVIEW

2.1 Study Design

This is an open-label, non-controlled, multicentre, pilot clinical trial of inhaled molgramostim in subjects with persistent pulmonary NTM infection.

The study will comprise a Screening Visit, Baseline Visit, a 48-week treatment period and a 12-week follow up period. The Screening Visit (Visit 1) will be conducted up to 10 weeks prior to the Baseline Visit (Visit 2) to determine eligibility. Adult subjects with a history of chronic NTM infection with at least 2 positive cultures in the prior two years, of which at least one is within the last 6 months prior to Screening, will be considered for enrolment. Subjects should provide a positive NTM sputum culture at Screening to be eligible.

The study will include 30 subjects.

The treatment period will consist of 14 trial visits (Screening, Baseline, and at Weeks 4, 8, 12, 16, 20, 24, 28, 32, 36, 40, 44, and 48; Visits 1-14) and a follow-up visit (Visit 15) 12 weeks after end of treatment. The visits at Weeks 28, 36 and 44 (Visits 9, 11 and 13) will include a telephone contact, all other visits will include a clinic visit.

At the Baseline Visit (Visit 2), eligible subjects will start treatment with inhaled molgramostim administered via the PARI eFlow nebulizer.

At each visit (Visits 1-15), sputum samples for staining and microscopy, and microbiological culture will be collected. If required, induced sputum may be obtained according to local standards. On the days of clinic visits (Visits 1, 2, 3, 4, 5, 6, 7, 8, 10, 12, 14 and 15), subjects will be asked to collect two additional sputum samples at home, preferably on the consecutive days after the site visit (At the commencement of the study, only 1 sample was required for Visits 2 to 7, with the additional sampling added in protocol amendment(s)). On the days of the telephone contact visits (Visits 9, 11 and 13), three sputum samples will be collected at home, preferably on consecutive days.

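### The TEAE window ends at a visit with no link to dosing, and no AE table separates on-drug from off-drug events

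*SAP*

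**What the plan says.** SAP 10.2.1 defines a treatment-emergent adverse event (TEAE) as "an AE that commences on, or after, the date of the first administration of study drug" and runs the window "until and including the day of the 12-week Follow-up visit". Last dose plays no part. Under SAP 10.2.2 the summary tables (by system organ class and preferred term, severity and relatedness) are built on TEAEs, while listings carry every recorded event. No table divides events by whether the subject was on drug.

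Three other provisions bear on this.

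- **Early stoppers.** Protocol 9.3.1: "Those who discontinue treatment will not automatically be withdrawn from the trial but will be encouraged to continue to follow the same visit schedule". Its example is a stop at Week 4.
- **Timing of Visit 15.** Protocol Table 1 places Visit 14 at "336 days after V2" and Visit 15 at "84 days after V14". The narrative in SAP 2.1, like Protocol 8.1, speaks of "a follow-up visit (Visit 15) 12 weeks after end of treatment".
- **Re-starters.** Under Protocol 8.1 and SAP 2.1, subjects who finished 24 weeks before Version 4.0 was approved go into the 12-week follow-up of Version 2.0 or 3.0 and may then re-start: "This will occur at the next trial visit or at an unscheduled visit". The second course lasts 24 weeks less the weeks already spent in follow-up.

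SAP Section 8 anticipates re-starters by deriving the number with a treatment break after Week 24. The AE section does not mention them.

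**The concern.** For a subject treated without interruption to Week 48, the rule amounts to last dose plus about 12 weeks. The trial also creates two kinds of subject for whom it means something else: those who stop early and stay on the schedule, and those who stop at Week 24 and start again.

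In both, drug-free time is pooled with time on drug in the only AE tables planned. The trial has no control arm, names no adverse events of special interest (Protocol 12.17.3) and sets no safety criteria for its review committee (Protocol 8.4.1). Protocol 6.3 says that more adverse effects than in alveolar proteinosis cannot be excluded. The TEAE tables therefore carry much of the safety conclusion, and a reader will want to know which events arose on drug.

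There is also an ambiguity. A re-starter may attend a follow-up visit after each course, and the definition does not say which one closes the window.

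**Working it through.** **Inputs.** Visit 14 at day 336 and Visit 15 84 days later (Protocol Table 1); screening up to 10 weeks (Protocol 8.1.1); stop at Week 4 (Protocol 9.3.1); second course of 24 − f weeks after f weeks in follow-up (Protocol 8.1).

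**Reproducing the plan's own figure.** (336 + 84) / 7 = 60 weeks; adding up to 10 weeks of screening gives 70. This matches the 60 to 70 weeks of participation in Protocol 8.1.1, so on the Table 1 schedule the window closes at Week 60.

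**Early stoppers on the Table 1 schedule.** Drug-free weeks in the window = (420 − stop day) / 7.

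| Stop | Drug-free weeks | Share of 60 weeks |
|---|---|---|
| Week 4 (day 28) | 392 / 7 = 56 | 93% |
| Week 8 (day 56) | 364 / 7 = 52 | 87% |
| Week 12 (day 84) | 336 / 7 = 48 | 80% |
| Week 24 (day 168) | 252 / 7 = 36 | 60% |
| Week 48 (day 336) | 84 / 7 = 12 | 20% |

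The Week 4 case is an example, not the limit: stopping just after the first dose gives about 60 weeks. If Visits 14 and 15 each fall 7 days late, every drug-free figure rises by 2 weeks.

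**Early stoppers if follow-up runs from each subject's own end of treatment.** The drug-free part is 12 weeks whenever the stop occurs. A Week 4 stopper's window would then end at Week 16, with 12 of 16 weeks (75%) off drug.

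**Re-starters.** Treatment ends at 24 + f + (24 − f) = Week 48 for every f, and weeks on drug are 24 + (24 − f) = 48 − f. The first follow-up visit falls at 24 + 12 = Week 36 and Visit 15 at Week 60. With f = 12 (re-start at the first follow-up visit), weeks on drug = 36.

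- *Window closed by Visit 15:* no on-drug week is lost. Drug-free weeks counted = f + 12 = 24 of 60 (40%), of which 12 are the gap between courses.
- *Window closed by the Week 36 visit:* 48 − 36 = 12 on-drug weeks fall outside, which is 12 / 36 = 33% of time on drug and the whole second course. The later 12-week follow-up is outside too.
- *Earlier re-start, Week 36 visit still held and used as the close:* the same 12 weeks are lost, or 12 / 16 = 75% of the second course at f = 8 and 12 / 20 = 60% at f = 4.

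**The case against.** The strongest reply is that a window running to the end of follow-up is what the protocol asks for. The safety endpoint counts events over the trial period (Protocol 7.3.2, SAP 10.1), Protocol 13.3 has all AEs summarised, and collection runs to Visit 15 (Protocol 12.16). That stands. It also counts against shortening the window to a fixed time after last dose: a Week 4 stopper's later events would leave every table. The short half-life (about 4 hours, Protocol 6.1) does not settle where the window should end either, since antibodies are still being measured at follow-up.

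Three stronger readings might be inferred, and the documents do not support them.

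- *That the SAP drops events during re-treatment.* Protocol 12.16 identifies the 12-week follow-up visit as Visit 15, and SAP Table 3 has a single follow-up visit, 15.0, after Week 48. On that reading the second course is inside. The loss needs the less natural reading; loss of the entire second course also needs a re-start at the Week 36 visit rather than earlier at an unscheduled one.
- *That 56 drug-free weeks is a firm figure or a maximum.* It is the protocol's example under one of two readings of Visit 15. Early stoppers are encouraged, not required, to keep attending.
- *That the trial could not say what happened on drug.* All events are listed, onset dates are recorded, and treatment discontinuation dates are listed (SAP Section 6). The information exists but is not summarised.

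What remains is that no planned table makes the separation, and that the definition leaves the closing visit for a re-starter to inference.

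**Conclusion.** The point holds as a gap in definition and presentation. Under the Table 1 schedule, drug-free time makes up 20% of the TEAE window for a 48-week completer, 40% for a re-starter with a 12-week gap and 93% for a Week 4 stopper who attends every visit. The last figure assumes that Visit 15 stays at Week 60; the per-subject reading gives 12 drug-free weeks instead. Table 1, Protocol 9.3.1 and the narrative in SAP 2.1 and Protocol 8.1 should be reconciled on this.

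Loss of re-treatment events from the tables, up to 12 of 36 on-drug weeks, is possible only if the Week 36 visit is taken as the close. It would not affect the listings. The documents do not give the number of early stoppers or re-starters, so the effect on the tables as a whole cannot be sized.

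This is a cheap improvement, not an error that invalidates the safety analysis.

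**What to change.** In SAP 10.2.1:

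1. Keep the wide window, so that events throughout the trial period stay in the tables.
2. State that it closes at the subject's last follow-up visit (Visit 15, after the final treatment course), or at end of participation if that visit is not attended. The present definition gives no closing date for a subject who never attends.
3. State how Visit 15 is timed for early stoppers, once the sponsor has reconciled the passages named above.

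In SAP 10.2.2, add an on-treatment/off-treatment split by onset date to the TEAE tables. On-treatment would mean any course from its first dose to a pre-stated number of days after its last dose; off-treatment would be the rest, including the remaining gap between courses. Thirty days is one option, since the protocol already uses that interval for contraception, but it is a reporting choice and another value fixed in advance would serve. With 30 days, a Week 4 stopper on the Table 1 schedule has 28 + 30 = 58 days on-treatment and 420 − 58 = 362 days off-treatment, all still tabulated.

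The cost is one derived flag and extra table columns. The sponsor should confirm that first-course stop dates and re-start dates can be derived: SAP Section 6 lists a single treatment discontinuation date, although the treatment-break count in Section 8 already depends on identifying the gap.

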10.3 Deaths

All details relating to subject deaths will be presented in a Death listing.

10.4 Prior and Concomitant Medication

Concomitant therapies will be coded using the World Health Organization-Drug Reference List (WHODRL).

Prior and concomitant medications will be presented in separate listings. Medications stopped on the same day as first study drug administration will be considered as prior medication only. Both prior and concomitant listings will flag antimycobacterial treatments and include data related to changes of the patient's NTM treatment regimen and the reason for a change to patient's NTM treatment regimen.

Prior and concomitant medication summaries will be presented in separate tabulations, with data summarised by Anatomical Therapeutic Chemical (ATC) (Level 2) and Preferred Name (PN) using frequency counts and percentages. For the summaries of prior and concomitant medications, subjects who take the same medication (in terms of the PN) more than once will be counted only once for that medication. An additional concomitant medication table will be prepared to present antimycobacterial treatments.

10.5 Laboratory

10.5.1 *Definition of variables*

10.5.1.1 *Hematology*

- Basophils (absolute and %)
- Eosinophils (absolute and %)
- Hematocrit
- Hemoglobin
- Lymphocytes (absolute and %)
- MCH
- MCHC
- MCV
- Monocytes (absolute and %)
- Neutrophils (absolute and %)
- Platelet count
- Red blood cell count (RBC)
- Red Cell Distribution Width (RDW)
- White blood cell count (WBC)

10.5.1.1 *Chemistry*

- Alanine Aminotransferase (ALT)
- Albumin
- Alkaline phosphatase
- Aspartate Aminotransferase (AST)
- Calcium
- Chloride
- C-Reactive Protein (CRP)
- Estimated glomerular filtration rate (eGFR)
- Gamma Glutamyl Transpeptidase (GGT)
- Glucose
- Lactate dehydrogenase (LDH)
- Phosphate
- Potassium
- S-Creatinine
- Sodium
- Total bilirubin
- Total protein
- Urea

10.5.1.1 *Urinalysis with Microscopy*

- Glucose
- Microalbuminuria
- pH
- Protein
- Red Blood Cells (RBC)
- White Blood Cells (WBC)

10.5.1.2 *Coagulation*

- PT-INR

10.5.2 *Biostatistical methods*

All laboratory parameters will be listed with flags for values outside the reference ranges and values considered to be clinically significant.

Each parameter will be summarised descriptively (including actual values and changes from baseline) for each scheduled visit. Shift tables will also be presented for hematology and chemistry variables.

10.6 Vital Signs

10.6.1 *Definition of variables*

- Systolic Blood Pressure (SBP) (mmHg)
- Diastolic Blood Pressure (DBP) (mmHg)
- Heart rate (beats per minute)
- Respiratory Rate (breaths per minute)
- Body temperature (°C)

10.6.2 *Biostatistical methods*

Vital sign parameters will be listed for all subjects and time points, including assessment (normal, abnormal) and clinical significance (clinically significant, not clinically significant).

Observed values, as well as changes from baseline, will be summarised descriptively for all vital sign parameters for each planned assessment.

10.7 Body Measurements

10.7.1 *Definition of variables*

- Weight (kg)
- Height (cm) (Baseline only)

10.7.2 *Biostatistical methods*

Height and weight will be listed for all subjects and time points.

Refer to Section 9.3.2.6 regarding presentation of post-Baseline weight data.

10.8 Physical Examination

10.8.1 *Definition of variables*

- | | |
|------------------------------------------|------------------|
| • General appearance | • Abdomen |
| • HEENT (Head, Eyes, Ears, Nose, Throat) | • Extremities |
| • Neck | • Dermatological |
| • Cardiovascular | • Neurological |
| • Respiratory | • Other |

10.8.2 *Biostatistical methods*

Physical examination data will be listed for all subjects and time points.

10.9 12-lead ECG

10.9.1 *Definition of variables*

- Heart rate (beats/minute)
- QRS interval (msec)
- PR interval (msec)
- QT interval (msec)
- ECG status (Normal/Abnormal) (Clinical significance will be flagged where abnormal)

10.9.2 *Biostatistical methods*

ECG parameters will be listed for all subjects and time points.

Observed values and change from baseline will be summarised descriptively for all ECG parameters for all planned assessments.

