## 12.11. Electrocardiogram (ECG)

A 12-lead ECG will be assessed using a standard ECG machine according to local procedures at the time points shown in [Table 1](#).

No central overreading will be performed.

Heart rate, QRS, PR and QT intervals will be recorded from the ECGs. The ECGs will be interpreted and signed and dated by the investigator or his/her designee. Results will be classified as normal, having a non-clinically significant abnormality, or having a clinically significant abnormality. All clinically significant abnormalities will be recorded as AEs.

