### **12.17.4. Precautions/Overdose**

No acute systemic or hypersensitivity reactions have been reported in subjects receiving inhaled sargramostim or molgramostim products.

There is no known antidote to molgramostim. In the event of overdose, symptomatic management is indicated.

Based on information from similar products, overdose may manifest with respiratory symptoms, e.g. bronchospasm, wheezing, dyspnea, decreased pulmonary function or cough.

Hematologic findings such as leukocytosis, eosinophilia and neutrophilia may occur in case of systemic exposure. With high systemic doses of similar products, the following symptoms have been observed: tachycardia, hypotension, dyspnea, and flu-like symptoms. These symptoms abated quickly on symptomatic treatment. More information is available in the IB.

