Any AEs will also be collected at Baseline and all subsequent visits (Visits 2-15), At all clinic visits a pregnancy test/contraceptive check will be conducted, changes in concomitant medication, measurement of body weight and an assessment of DLCO will be performed. A computed tomography (CT) scan will be conducted at Baseline (Visit 2) if not performed within 6 months prior to Baseline. If DLCO drops by at least 20% at two consecutive visits the CT scan may be repeated. A CT scan can be performed after 48 weeks of treatment if this is a part of the local routine clinical practice.

A physical examination and an electrocardiogram (ECG) will be performed at Screening and Weeks 24 and 48 (Visits 1, 8 and 14) and vital signs will be collected at Screening, Baseline, and Weeks 4, 12, 24, 32, 40 and 48 (Visits 1, 2, 3, 5, 8, 10, 12 and 14). Spirometry will be conducted at Baseline and at Weeks 12, 24, 32, 40 and 48 (Visits 2, 5, 8, 10, 12 and 14). A

6MWT will be conducted at Baseline, at Weeks 12, 24 and 48 and at the 12-week follow-up visit (Visits 2, 5, 8, 14 and 15). Blood samples for safety laboratory testing will be taken at Screening, Baseline, and at Weeks 4, 12, 24, 32, 40, 48 and at the 12-week follow-up visit (Visits 1, 2, 3, 5, 8, 10, 12, 14, 15). Anti-GM-CSF will be assessed at Baseline, at Week 4, 12, 24, 32, 48 and at the 12-week follow-up visit (Visits 2, 3, 5, 8, 10, 14 and 15). Subject reported outcomes (QoL-B, LRTI-VAS and GRH) will be assessed at Baseline and at all post Baseline clinic visits (Visits 2, 3, 4, 5, 6, 7, 8, 10, 12, 14 and 15). For subjects having a chest X-ray during the study period as part of the routine local clinical practice, the results from the X-ray will be recorded.

Participating subjects will be encouraged to contact the clinic between visits if they experience adverse events (AEs), worsening of their condition or have any other concerns. If needed, unscheduled visits will be conducted at investigator's discretion.

Treatment with inhaled molgramostim will be given at a dosage of 300 µg once daily for 48 weeks. All subjects in the trial initially consented to 24 weeks of treatment. All enrolled subjects continuing with 48 weeks of treatment will re-consent and follow the visits schedule as described above.

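### The ECG table summarises QT without heart-rate correction, so its change from baseline cannot be separated from a change in heart rate; deriving QTcF from data already recorded would fix this.

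*SAP*

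**What the plan says.** Protocol 12.11 fixes what is captured: "Heart rate, QRS, PR and QT intervals will be recorded from the ECGs". ECGs are done and read locally ("No central overreading will be performed"). The investigator or a designee classifies each tracing, and "All clinically significant abnormalities will be recorded as AEs".

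SAP 10.9.1 carries the same four measurements into the analysis, including "Heart rate (beats/minute" and "QT interval (msec", plus a normal/abnormal status. SAP 10.9.2 then states: "Observed values and change from baseline will be summarised descriptively for all ECG parameters for all planned assessments". On timing, SAP 2.1 says "A physical examination and an electrocardiogram (ECG) will be performed at Screening and Weeks 24 and 48". Under SAP 3.3.3, baseline is the last assessment before first dose, which on this schedule is the Screening ECG.

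Neither document names a corrected QT, a correction formula or any other analysis of QT that accounts for heart rate. ECG intervals are not among the safety endpoints in Protocol 7.3.2 or SAP 10.1.

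**The concern.** Raw QT varies inversely with heart rate. A change from baseline in raw QT is therefore the sum of a rate effect and any change in repolarisation, and the table as planned shows only the sum.

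This can mislead in two directions. If heart rate rises on treatment, a true lengthening can appear as no change. If heart rate falls, raw QT lengthens and can look like a repolarisation effect when there is none. In a controlled trial a rate shift common to both arms would largely cancel. Here the only comparison is with the subject's own baseline, taken up to 10 weeks before first dose, so a systematic rate shift passes straight into the QT change.

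What is at stake is whether one descriptive safety table can be interpreted. No endpoint or decision rule in either document depends on it.

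**Working it through.** The plan states no figure on this point, so there is nothing to reproduce. The documents also give no QT or heart-rate values, so every input below is an assumption chosen to show scale.

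**Formula.** With RR = 60/heart rate in seconds, Fridericia's correction is QTcF = QT/RR^(1/3), so QT = QTcF × RR^(1/3).

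**Step 1: a rate shift with no change in repolarisation.** QTcF is held constant and heart rate moves 10 bpm from 70.

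| Assumed QTcF (ms) | Raw QT at 60 bpm | Raw QT at 70 bpm | Raw QT at 80 bpm | 70 to 60 | 70 to 80 |
|---|---|---|---|---|---|
| 400 | 400.0 | 380.0 | 363.4 | +20.0 | −16.6 |
| 420 | 420.0 | 399.0 | 381.6 | +21.0 | −17.4 |
| 440 | 440.0 | 418.0 | 399.8 | +22.0 | −18.2 |

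The planned table would report a raw QT change of about 17 to 22 ms in absolute size although nothing happened to repolarisation.

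**Step 2: a repolarisation change with no change in raw QT.** Raw QT is held constant, so the planned table shows zero change.

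- Raw QT 380 ms, 70 to 80 bpm: QTcF goes from 380 × (70/60)^(1/3) = 400.0 to 380 × (80/60)^(1/3) = 418.2 ms. The hidden rise is about 18 ms. From 70 to 75 bpm it is about 9 ms, and from 70 to 85 bpm about 27 ms.
- Raw QT 410 ms, starting at 60 bpm: QTcF goes from 410.0 to 431.6 ms at 70 bpm and 451.3 ms at 80 bpm. The hidden rises are about 22 and 41 ms.

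**Step 3: keep the two quantities apart.** The fall in raw QT at constant QTcF (Step 1) is not the prolongation hidden when raw QT stays flat (Step 2). At an assumed QTcF of 410 ms, raw QT falls from 410.0 ms at 60 bpm to 389.5 at 70 and 372.5 at 80, which is 20.5 and 37.5 ms. The corresponding hidden rises are the 22 and 41 ms above.

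**Step 4: dependence on the formula.** With Bazett's exponent of 1/2, the Step 1 range becomes about 24 to 33 ms, and the 380 ms example at 70 to 80 bpm becomes about 28 ms. Fridericia gives the smaller figures here.

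**The case against.** The strongest reply is that this is routine monitoring in a small pilot and that the plan already covers much of the gap. That is partly right.

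- **Heart rate is summarised too.** SAP 10.9.2 covers ECG heart rate with change from baseline, SAP 10.6 covers vital-sign heart rate, and all ECG values are listed. A large group shift would be visible, and a reader could compute QTcF from the listing or approximate its mean from the group means. What separate summaries do not give is each subject's corrected change, or its SD, minimum and maximum. The correction is non-linear and has to be made per ECG.
- **Investigators classify each ECG.** This may catch individual outliers, but no QT criterion is stated and it does not repair the group table.
- **Correction would not turn this into a QT assessment.** This stands. There are 30 planned subjects in two groups, no control, three scheduled ECGs and local reading. Protocol 11.5 puts the last dose on the day before the Week 48 visit, and Protocol 6.1 reports a half-life of about 4 hours. No ECG time relative to dosing is set at Week 24.

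Three stronger readings are tempting, and the documents do not support them.

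- A reader might infer that a heart-rate rise is to be expected, because Protocol 12.17.4 says "the following symptoms have been observed: tachycardia, hypotension, dyspnea, and flu-like symptoms". That sentence concerns high systemic doses of similar products. Protocol 6.1 puts systemic levels after inhalation at 50 to 100 times below those after similar intravenous doses of sargramostim. Protocol 6.3 does say that higher exposure in NTM than in PAP cannot be excluded, but that is not evidence of a rate effect at this dose.
- A reader might infer that the table would miss QT prolongation from the antimycobacterials. Neither document says that they affect QT. Group 1 has also been on its regimen for at least 6 months before Baseline, so any effect of a stable regimen would already be in the baseline ECG, corrected or not.
- A reader might infer that correction would show whether the drug prolongs QT. Without a control, a change in QTcF still could not be attributed to the drug.

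**Conclusion.** The point holds in a limited form. As planned, the change in raw QT cannot be separated from a change in heart rate, although both values come from the same tracing. The illustrated distortion, about 17 to 22 ms for a 10 bpm shift from 70 bpm, rests on assumed QTcF values of 400 to 440 ms and on Fridericia's formula. It shows what the table could confuse, not what is likely to occur in this trial. The documents give no reason to expect a QT effect or a shift of that size. Severity is minor: a descriptive safety table that is not a listed endpoint becomes easier to read, and no conclusion on efficacy is touched.

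**What to change.** In SAP 10.9.1, add a derived variable QTcF (msec) = QT/(60/heart rate)^(1/3), calculated for each ECG from the QT and heart rate of that same tracing, and left missing if either is missing, in line with SAP 12. In SAP 10.9.2, list it and summarise observed values and change from baseline at each planned ECG, beside raw QT. State in the table note that the comparison is uncontrolled and descriptive.

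The cost is one derived variable and a few extra rows in an existing table. It needs no new data, no additional visits and no protocol amendment. The SAP already makes this kind of derivation in 10.10, where percent-predicted values are calculated for DLCO and spirometry.
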